2.2 Secondary Objectives (or Aim)

There are three secondary objectives:

- (1) To determine the impact of poor child sleep (short sleep duration, later bedtimes, inconsistent bedtimes, night wakings, and poor sleep quality) on daily child behavior, caregiver mood, and caregiver sleep.
 - Hypothesis 2a: Worse child sleep on one night will be associated with worse child behavior and diminished caregiver nighttime sleep and caregiver mood the following day.
 - Hypothesis 2b: The effects of poor sleep will be cumulative, such that children with poor sleep across multiple nights will exhibit the worst child behavior, with the lowest caregiver mood and worst caregiver sleep, over the two-week study period.
- (2) To determine the impact of provision of a child bed through the Beds for Kids program on child sleep at one-month follow-up (one-month post-bed delivery).
 - Hypothesis 3a: Receiving a bed will be associated with improved sleep health (longer total sleep, earlier bedtimes, more consistent bedtimes, decreased night wakings, and better sleep quality) from baseline to one-month follow-up across study conditions.
- (3) To identify caregivers' perceptions of barriers and facilitators related to sleep health and potential behavioral sleep treatment (one-month post-bed delivery).
 - This is an exploratory aim.

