6.3.2 Efficacy Analysis

The primary analysis will be based on an intention to treat approach and will include all randomized subjects. To evaluate the impact of provision of a child bed through the Beds for Kids program on child sleep (Hypothesis 1a), we will compare children in the study condition who received a bed at day 7 to those in the waitlist control condition (bed at day 14) on objectively and subjectively measured sleep variables using two-level multilevel mixed models. Multilevel models allow for an examination of both within-child (daily assessments, level 1) and between-child (level 2) associations between sleep and daily child and/or caregiver functioning.²⁰ Child age, sex, baseline caregiver mood and resilience, and family chaos as level 2 covariates, given research showing that these variables impact child sleep. ^{7, 9, 12} To examine whether children who receive a bed at day 7 show improved behavior, increased caregiver mood, and better caregiver sleep relative to children in the waitlist condition (Hypothesis 1b), we will run three different multilevel mixed effect models, using child daily behavior, caregiver mood, and caregiver sleep scores as the outcomes, respectively. Analyses will include child sleep location, age, sex, baseline caregiver mood and resilience, baseline family chaos, and baseline child internalizing and externalizing behavior at model level 2 as covariates.

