Aim 2: To determine the impact of poor child sleep (short sleep duration, later bedtimes, inconsistent bedtimes, night wakings, and poor sleep quality) on daily child behavior and caregiver functioning (mood and sleep) (Hypothesis 2a), we will specify two-level multilevel models. We will use data from week 1 of the study, as at that time children in both conditions will not have received a bed through the Beds for Kids program. We will also specify models using 2-week data from those in the intervention group to assess whether improved sleep after week 1 as a result of receiving a bed also leads to improved functioning. In these models, each child sleep variable is entered as a predictor of each of the functional outcomes at level 1. Child behavior, caregiver mood, and caregiver sleep variables will be specified as outcomes in separate models. Covariates (as described for Aim 1) will be added to level 2. This multi-level modeling approach is consistent with other studies assessing associations between sleep and next-day child functioning.²⁰ To test whether the effects of poor sleep are cumulative (Hypothesis 2b), with children with poor sleep across multiple nights exhibiting the worst behavior, lowest caregiver mood scores, and worst caregiver sleep, we will run separate two-level multilevel models by outcome with averaged (cumulative) child sleep variables across week 1 nights as the predictors of

average child behavior, caregiver mood, and caregiver sleep ratings across this period. Child age, sex, baseline behavior, baseline family chaos, and baseline caregiver mood and resilience will be entered as level 2 covariates.

Aim 3: To determine whether provision of a child bed is associated with improved sleep health (longer nighttime sleep, earlier bedtimes, more consistent bedtimes, decreased night wakings, and better sleep quality) from baseline to one-month follow-up across study conditions (Hypothesis 3a), we will regress each follow-up sleep outcome on the baseline sleep outcome, with covariates including child age, child sex, study condition (to control for amount of time child has had the bed), and baseline caregiver mood and resilience, family chaos, and child behavior.

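### Hypothesis 2b relates week-average sleep to week-average functioning, a between-child association that cannot separate accumulation from a repeated one-night effect

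*Combined protocol and SAP*

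**What the plan says.** Section 2.2 separates two hypotheses under the first secondary objective. Hypothesis 2a concerns one night's sleep and the following day. Hypothesis 2b goes further: "The effects of poor sleep will be cumulative, such that children with poor sleep across multiple nights will exhibit the worst child behavior". Its time frame is given as "over the two-week study period".

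Section 6.3.2 (Aim 2) sets out the test of 2b. The models are called two-level, are run separately for each outcome, and take "averaged (cumulative) child sleep variables across week 1 nights as the predictors of" functioning. The outcomes are likewise weekly means, described as "average child behavior, caregiver mood, and caregiver sleep ratings across this period". Predictor and outcome are therefore both averages over week 1. The adjustment is: "Child age, sex, baseline behavior, baseline family chaos, and baseline caregiver mood and resilience will be entered as level 2 covariates". The same section defines the levels as "within-child (daily assessments, level 1) and between-child (level 2) associations".

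No lagged sleep term, running count of poor nights or contrast with the one-night effect is specified for 2b. Section 6.4 gives no sample size for 2b. Its figure of 25 participants is for daily effects of sleep on mood.

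**The concern.** There are two problems, and the second matters more.

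- **Structure.** If the averages are computed first, each child has one predictor value and one outcome value. The daily level is then empty, and a two-level model cannot be fitted as described. No other clustering unit is named: models are run separately by outcome, with no site level.
- **Interpretation.** An average over nights is not a measure of accumulation. If each day depends only on the night before, a child with worse nights on average will also have worse days on average. A stable feature of the child or household that affects both sleep and functioning gives the same pattern.

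A significant coefficient would invite the conclusion that the effects of poor sleep are cumulative, which this analysis cannot support.

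**Working it through.** **The plan's own figure.** The 25 participants in section 6.4 can be reproduced by reading .35 as Cohen's f². Then λ = 0.35 × 25 = 8.75, and a one-predictor F test at two-sided 5% has power 0.809. That figure is not in dispute, but it does not size 2b. With 50 rows and 6 to 8 covariates, the averaged regression has about 73% power for a partial correlation of .35 and 94% for .45.

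**Inputs.** From the documents: 50 dyads and 7 nights in week 1. Assumed, because the documents give no values: unit-variance sleep with intraclass correlation (ICC) 0.5, unit-variance outcome residual with ICC 0.5, and the effect sizes below.

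**Step 1: rows left after averaging.** With both sides averaged over week 1, the within-child variance of the outcome is exactly 0, and 50 children give 50 distinct rows.

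**Step 2: slope with no carry-over.** Let the daily outcome be Y = b × (last night's sleep) + u + e, with child effect u and daily error e. Averaging over the week gives mean Y = b × (mean sleep) + u + mean e. If u is unrelated to sleep, the averaged slope is b, whatever the ICC. Simulation agrees: b = 0.35 returns 0.349 to 0.360, and b = 0.45 returns 0.450 to 0.452, for sleep ICC 0.3 to 0.7.

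**Step 3: how often the test is then significant.** Variance of mean sleep = 0.5 + 0.5/7 = 0.571, and the residual variance of the mean outcome is the same. The noncentrality is about b × √50, which is 2.12 for b = 0.30 and 3.18 for b = 0.45. The critical value is about 2.01 on 48 degrees of freedom. Simulated rates, with no accumulation present:

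| One-night effect | Averaged test significant | Prior-two-nights term significant |
|---|---|---|
| 0.30 | about 54% | about 6% |
| 0.45 | about 86% | about 6% |

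For an effect of 0.30, the averaged test ranges from 40% to 66% as sleep ICC goes from 0.3 to 0.7.

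**Step 4: two mechanisms, one answer.** Take a truly cumulative process: 0.10 for last night plus 0.10 for each of the three nights before. The covariance of each lagged weekly mean with the week-1 mean is 0.5 + 0.5 × (7 − k)/49, which is 0.561, 0.551 and 0.541 for k = 1, 2, 3. These sum to 1.653, and 1.653/0.571 = 2.89. The expected averaged slope is 0.10 + 0.10 × 2.89 = 0.389 (simulated 0.385). A pure one-night effect of 0.385 also gives a simulated slope of 0.385. The rejection rates are 73% and 75%, so the planned coefficient does not tell the two apart.

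**Step 5: can the daily data do so?** In simulation, a within-child model with last night's sleep and the mean of the preceding two nights has about 71% power for a two-night-mean effect of 0.30 (51% to 84% as sleep ICC goes from 0.7 to 0.3). Power is about 41% for an effect of 0.20. A three-night mean with effect 0.30 has only about 31%.

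**The case against.** Five points can be made for the plan.

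- **The model may be identified.** The section defines level 1 as days and enters covariates at level 2, so daily rows with child means at level 2 may have been intended. That model can be fitted, and a reader should not conclude that the analysis is impossible. The text does not say this was meant, however, and the child-mean slope would still be between-child.
- **The hypothesis explains itself.** It describes children with poor sleep over multiple nights as functioning worst, and the averaged regression does address that clause. This stands. What is unsupported is the word cumulative, which both sections use.
- **The one-night effect is estimated as well.** Hypothesis 2a uses daily sleep at level 1, so it would be wrong to infer that Aim 2 as a whole discards the daily data. No contrast between the two slopes is planned, though, and between-child confounding could also make them differ.
- **The rates are not false positives.** A reader might set 54% to 86% against a nominal 5%. The null of the averaged test is no association between mean sleep and mean functioning. That null is false in these scenarios, so rejecting it is correct. Under a true null the rate is about 5%.
- **The plan adjusts for household factors.** Family chaos, caregiver mood, resilience and baseline behavior are covariates, so an unadjusted confounding figure would not describe the planned model. With an assumed shared factor carrying 40% of between-child variance, simulated rejection is about 70% unadjusted. It falls to 31%, 15% and 7% if a covariate captures 50%, 70% or 90% of that factor. Residual confounding is possible, but the documents give no basis for its size.

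**Conclusion.** The concern holds for the claim of accumulation. As written, the test of Hypothesis 2b estimates a between-child association and cannot support a cumulative conclusion. The equality of slopes in step 2 is algebra and needs no assumed ICC. The 54% to 86% range depends on the assumed ICC and effect sizes, and it measures non-specificity for accumulation only.

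Whether level 1 is truly empty depends on what was meant by averaging. Literally it is, but the main conclusion does not rest on that.

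This is one sub-hypothesis of a secondary objective in a study that calls itself a pilot. The primary endpoint is unaffected. The plan should be changed because a routine significant result would otherwise be misread.

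**What to change.** 1. Fit the average-on-average analysis as a single-level regression with one row per child and the planned covariates. Report it as a between-child association and do not call it cumulative. If daily rows with child means at level 2 were intended, state that model explicitly and use the same label.
2. For the cumulative claim, keep daily outcomes at level 1. Pre-specify one history term, the mean of the preceding two nights, adjusted for last night's sleep, with both centred within child. Put the child's week mean and the planned covariates at level 2, and test Hypothesis 2b on the history term.
3. Apply step 2 only to sleep variables that have a nightly value. Bedtime inconsistency is defined only across nights and stays a between-child analysis.
4. Align the time frame: section 2.2 states the hypothesis over two weeks, while section 6.3.2 uses week 1.

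**Cost.** No new data are needed, but this is more than rewording. Two of seven nights are lost to the lag, before any missing diaries or actigraphy. Power is limited: about 71% for a two-night-mean effect of 0.30 under the assumptions above, and lower for smaller effects. A null history term should therefore be reported as inconclusive, not as evidence against accumulation.

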3.1.3 Follow-up Phase

Caregivers in both study conditions will complete follow-up measures at one-month after bed delivery (visit 15; day 35 [+1-7 days] for intervention participants or day 42 [+1-7 days] for waitlist control participants). Study duration at follow-up for baseline surveys is approximately 30 minutes. At follow-up, families will also be given the option to verbally consent to participate in a brief (30-minute) semi-structured interview about sleep health and behavioral sleep treatment.

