4.3 Follow-up Phase (only if applicable)

Caregivers will be contacted at one-month follow-up post-bed delivery (study day 36 [+1-7 days] for the intervention condition; day 43 [+1-7 days] for the waitlist control condition) to complete follow-up measures and a brief, semi-structured qualitative interview. The study will then end.

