6.2 Secondary Endpoints

Secondary endpoints will include the following:

- The association between child sleep and next-day child behavior (Aim 2)
- The association between child sleep and next-day caregiver mood (Aim 2)

- The association between child sleep and caregiver sleep (Aim 2)
- The change in child sleep based on caregiver report at baseline and one-month follow-up (Aim 3)

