6.3 Statistical Methods

6.3.1 Baseline Data

Data for the primary objective and first two secondary objectives will be analyzed using Mplus Version 8.⁴⁶ Data will be summarized using descriptive statistics (means and percentages). We will examine the normality of the data and adjust analyses as needed.

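### The regression planned for Aim 3 contains no term that tests the mean change in sleep predicted by Hypothesis 3a

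*Combined protocol and SAP*

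**What the plan says.** Section 2.2 states Hypothesis 3a as an improvement in sleep health "from baseline to one-month follow-up across study conditions". Section 6.2 lists the matching endpoint: "The change in child sleep based on caregiver report at baseline and one-month follow-up (Aim 3"). Both describe a mean change pooled over the two arms.

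Section 6.3.2, under Aim 3, gives the analysis: "we will regress each follow-up sleep outcome on the baseline sleep outcome, with covariates including child age, child sex, study condition", together with baseline caregiver mood and resilience, family chaos and child behavior. For Aim 3 it states no paired test, change score, time term, centring or contrast on the intercept.

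Two other places might have supplied a test and do not. Section 6.3.1 promises only description: "Data will be summarized using descriptive statistics (means and percentages"). The repeated measures analysis of variance in Section 6.4 is for the comparison of the two groups.

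The condition covariate comes with a reason: "study condition (to control for amount of time child has had the bed"). Follow-up is set at one month after bed delivery in both arms. Section 3.1.3 puts it at "day 35 [+1-7 days] for intervention participants or day 42 [+1-7 days] for waitlist control participants", and Section 4.3 at "study day 36 [+1-7 days] for the intervention condition; day 43 [+1-7 days] for the waitlist control condition".

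**The concern.** Regressing follow-up on baseline is the usual way to compare arms with adjustment for baseline, but Hypothesis 3a is not an arm comparison. It asks whether the average child sleeps better at one month than at baseline. The fitted coefficients answer other questions: whether baseline sleep predicts later sleep, and whether two arms that both have beds differ at follow-up.

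The practical risk is misreading. The baseline slope will often be significant because a child's sleep at two times is correlated, and that result could be reported as support for the hypothesis. It would look the same if sleep had not changed or had become worse.

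**Working it through.** **Plan's own figures.** Section 6.4 gives no calculation for Aim 3; it says only that 50 dyads will suffice. Its figure for the two-group comparison, 24 subjects, can be reproduced by reading .45 as Cohen's f for the between-group factor: λ = 0.45² × 24 × 14 / (1 + 13 × 0.5) = 68.04 / 7.5 = 9.07, with 1 and 22 df, giving power 0.821. That is a different comparison and does not bear on this point.

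**Step 1: algebra.** Write the stated model as F = a + bB + cG + d′X + e, where F is follow-up sleep, B baseline sleep, G condition and X the other covariates. Replace F by F + k for every child. Least squares then gives a + k, with b, c, d, their standard errors and p-values unchanged. So no slope carries information about a uniform change. The intercept does move, but it is the expected follow-up value when all covariates equal zero. This step needs no assumption about the data.

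**Step 2: numerical check.** In one simulated data set, shifts of −1, 0, 0.5 and 1 all gave slope 0.2914 (p = 0.127) and condition 0.0558 (p = 0.871). The intercepts were 5.24, 6.24, 6.74 and 7.24.

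**Step 3: how often each term is significant.** Inputs: n = 50 (Section 3.3.2) and two-sided 0.05. Assumed, because the documents give no values: normal outcomes with unit SD, condition plus seven other covariates, and correlation ρ between baseline and follow-up of 0.3, 0.5 or 0.7. There were 10,000 replicates per setting.

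| | ρ = 0.3 | ρ = 0.5 | ρ = 0.7 |
|---|---|---|---|
| Baseline slope significant, no change | 49.8% | 93.3% | 100% |
| Baseline slope significant, +0.5 SD | 49.9% | 93.2% | 100% |
| Condition significant, all settings | 4.9–5.2% | 4.9–5.2% | 4.9–5.2% |

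In a separate run of 2,000 replicates at ρ = 0.5, the slope was significant in 94% of trials with no change and in 94% with a worsening of 1 SD.

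**Step 4: a direct test.** For a paired t test, d_z = δ / √(2(1 − ρ)), the noncentrality is d_z√50, and df = 49.

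| δ (SD) | ρ | d_z | Noncentrality | Power |
|---|---|---|---|---|
| 0.5 | 0.3 | 0.423 | 2.99 | 83% |
| 0.5 | 0.5 | 0.500 | 3.54 | 93% |
| 0.5 | 0.7 | 0.645 | 4.56 | 99% |
| 0.3 | 0.3 | 0.254 | 1.79 | 42% |
| 0.3 | 0.5 | 0.300 | 2.12 | 55% |
| 0.3 | 0.7 | 0.387 | 2.74 | 77% |

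Its simulated type I error in the 10,000-replicate runs was 4.9–5.2%.

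**Step 5: the reason given for the condition covariate.** Nominal time with the bed is 35 − 7 = 28 and 42 − 14 = 28 days by Section 3.1.3. By Table 1 and Section 4.3 it is 36 − 8 = 28 and 43 − 15 = 28 days. The arms do not differ on it. What differs is the nominal interval from baseline to follow-up, by 42 − 35 = 43 − 36 = 7 days.

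**The case against.** The best reply is that the information is in the fit. A least-squares model with an intercept passes through the sample means, so its prediction at the mean covariate values, less mean baseline sleep, equals the observed mean change. The plan does not rule out centring. That is correct, and the fault should be stated precisely: no contrast for mean change is named, and none of the coefficients serves as one.

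The contrast also needs care. If the change score is the outcome, baseline sleep is kept and every covariate is centred at its sample mean, the intercept estimates mean change but its default standard error treats the sample baseline mean as fixed. The residual variance is 1 − ρ², whereas the variance of a change is 2(1 − ρ), so the standard error is too small by a factor √((1 + ρ)/2): 0.806, 0.866 and 0.922 for ρ = 0.3, 0.5 and 0.7. With 1.96 as the cut-off, type I error is about 11%, 9% and 7%; simulation gave 10.7%, 9.0% and 7.0%. Dropping baseline sleep helps only if the other covariates do not predict change: simulated error was 5.1%, 7.4% and 8.5% when they explained 0%, 17% and 25% of its variance. Those shares are assumptions. Section 6.3.2 justifies several covariates as "given research showing that these variables impact child sleep", which concerns sleep itself and not change in sleep.

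Second, the means promised in Section 6.3.1 may cover follow-up as well as baseline and so show the direction and size of change. That also stands, but means alone do not test a stated hypothesis.

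Third, this is a secondary aim of a study that Section 2 calls a pilot. That limits the weight of the point but does not remove it. The wording about time with the bed is a small matter and changes no conclusion.

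**Conclusion.** The concern holds. As written, Aim 3 is tied to an analysis whose coefficients do not test its hypothesis, and no other section supplies the test. The result follows from the form of the model, whatever the sample size, correlation or effect. The percentages only illustrate it and rest on the assumed normal outcomes, correlations and effect sizes.

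This should be fixed before analysis. It concerns one secondary, uncontrolled before-after aim; the primary comparison of bed against waitlist is not affected.

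**What to change.** In Section 6.3.2, Aim 3, name one test of Hypothesis 3a for each sleep outcome: a paired test of follow-up minus baseline, or the time coefficient in a mixed model with two time points per child. With complete data the two agree. In a complete simulated data set the mixed model gave 0.5002 (SE 0.1260), equal to the paired test. They differ when follow-up is missing: the paired test uses complete pairs only, while the mixed model also uses children with a baseline value alone. Section 3.3.2 counts completers, so some enrolled children may lack follow-up, and the text should say which method applies then.

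Further wording:

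- Report the result as an uncontrolled before-after change, since both arms have beds at follow-up.
- Keep the regression of follow-up on baseline only to describe predictors of follow-up sleep.
- Do not rely on a sample-mean-centred change-score intercept with default standard errors.
- If change by arm is wanted, use a condition-by-time term and average over arms for the pooled test. A condition main effect does not adjust the change. Coding matters: in the simulated data set, 0/1 coding gave 0.4090 (SE 0.1791), the change in the reference arm alone, while −0.5/+0.5 coding gave the pooled 0.5002 (SE 0.1266).
- Correct the reason given for the condition covariate.

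The cost is one or two sentences for the test itself and a short wording correction. The baseline and follow-up questionnaires are already scheduled, and neither visits nor sample size change.
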